9.3.2 Definition of Analysis Sets

9.3.2.1 Screening Analysis Set

All patients who signed the inform consent and have performed Visit 1 (screening).

9.3.2.2 Randomized Analysis Set

All patients who signed the informed consent and were randomized by IRT will be included and analysed according to their randomized treatment arm / treatment sequence.

9.3.2.3 Full Analysis Set

All patients who signed the informed consent and are randomized and received at least 1 dose of IMP in the trial, will be included and analyzed according to their randomized treatment. The Full Analysis Set is the primary analysis set for all efficacy endpoints and patient reported outcome (PRO) assessment.

9.3.2.4 Safety Analysis Set

All patients from the Screening Analysis Set, who received at least 1 dose of IMP in the trial will be included in the Safety Analysis Set and analysed according to the treatment received. Only patients for whom it has been confirmed that they did not take IMP will be excluded from the Safety Analysis Set. The Safety Analysis Set will be used to report all safety data using the actual treatment arm.

9.3.2.5 Study Completer Analysis Set

All patients from the FAS who have completed the trial (completed both treatment period 1 and treatment period 2), regardless whether they have permanently withdrawn from study drug. The analyses on the Study Completer Analysis Set will only be conducted on efficacy endpoints and patients analyzed according to their randomized treatment arm.

9.3.2.6 Per Protocol Analysis Set

The Per Protocol (PP) Analysis Set is defined as follows: a subset of the FAS that includes all patients who have completed the trial with no major important protocol deviations deemed to compromise the assessment of efficacy. Major important protocol deviations will be identified as a subset of the important protocol deviations and fully defined prior to unblinding of the trial. The PP analysis will only be conducted on efficacy endpoints and patients analyzed according to their randomized treatment arm.

9.3.2.7 Pharmacokinetic Analysis Set

All patients who have received at least 1 dose of IMP and provided sufficient bioanalytical data to calculate reliable (based on the judgement of the pharmacokineticist) estimates of the PK parameters of THC, CBD, and their metabolites will be included in the PK Analysis Set. This analysis set cannot be determined before unblinded analysis.

10.0 Conventions and Derivations

10.1 Study Period, Reference Day, Study Day, Analysis Day and Visit Window

10.1.1 Study Periods

For each patient, there will be a screening period, an evaluable period composed of a treatment period 1, a washout period, and a treatment period 2, and a safety follow-up period.

The Screening period starts on the day of the informed consent signature and ends on Day 1 (as defined on in [Section 10.1.2](#)) before 1st IMP intake.

The evaluable period starts on the day of randomization and ends the day of the safety follow-up visit.

- The **51-day efficacy period** which starts on the first day of IMP administration and ends at the end of treatment date.
 - This period will be composed of:
 - The **21-day on-treatment efficacy Period 1** which starts the day of first IMP intake during Period 1 and ends the earliest between end of Period 1 D21 date and permanent end of treatment date;
 - The on-treatment **wash-out period** which begins the day following the end of the 21-day on-treatment efficacy Period 1 and ends the day before the beginning of the 21-day on-treatment efficacy Period 2;
 - The **21-days on-treatment efficacy Period 2** which starts the day of IRT call for Period 2 and ends on the end of treatment date. This period is only defined for patients exposed to IMP during Period 2.
 - It will be used for efficacy analyses using the Full Analysis Set.
- The **51-day safety period** which starts on the first day of IMP administration and ends at the end of treatment date (+ x days).
 - This period will be composed of:
 - The **21 day on-treatment Safety Period 1** which starts the day of first IMP intake during Period 1 and ends the earliest between end of the wash out period date, the day before the date of IRT call for Period 2, the day before Visit 6 date and permanent end of treatment date + x days.
 - The **21 day on-treatment Safety Period 2** which starts the earliest between date of Visit 6, day of IRT on treatment safety period call for Period 2 date, and ends on the end of treatment day date + x days.
 - x will be equal to 14 days for Adverse events, 4 days for C-SSRS and 0 days otherwise.
 - it will be used for safety analyses using the Safety Analysis Set (unless otherwise specified).
- The **Follow-up period** which starts the day following the 51-day on-treatment safety period and ends on the end of study date.

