Control Arm	All patients enrolled in the trial will receive both nabiximols and placebo during the 2-way crossover treatment period.

Procedures	
Assessments/procedures at the trial site include the following:
 
• Informed consent, demographics, previous cannabis use, medical history, electronic diary training, and blood THC test (Visit 1)• Eligibility check and urine drug screen (including THC) (Visits 1 and 2 [predose])• Randomization and IMP dosing training (Visit 2 [predose])• Concomitant medications review, AE review, and vital signs measurement (Visits 1, 2, 4, 5, 6, 8, 9, and 10)• Physical examination (including height measurement at Visit 1 only), 12-lead ECG, and clinical laboratory blood sampling (hematology and biochemistry) (Visits 1, 5, and 9)• Examination of oral mucosa (Visits 1, 2 [predose], 4, 5, 6 [predose], 8, 9, and 10)• Body weight measurement (Visits 1, 2 [predose], 6 [predose], and 10)• Dipstick urinalysis and serum pregnancy test (if appropriate) (Visits 1 and 10)• Urine pregnancy test (if appropriate) (Visits 2 and 6 [predose])• PK blood sampling (IMP) at distinct time points (Visits 2, 4, 5, 6, 8, and 9)• MAS assessment (Visits 1, 2 [predose and at 3 hours ± 15 minutes postdose], 5 [3 hours ± 15 minutes after the first spray of the morning dose], 6 [predose and at 3 hours ± 15 minutes postdose], and 9 [3 hours ± 15 minutes after the first spray of the morning dose])• MSSS-88 assessment (Visits 5 and 9)• T25FW test (Visits 2 [predose], 5, 6 [predose], and 9)• C-SSRS assessment (Visits 1, 2 [predose], 4, 5, 6 [predose], 8, 9, and 10)• IMP dosing at the investigational site (Visits 2, 5, 6, and 9)• IMP dispensing (Visits 2, 4, 6, and 8)• IMP collection and compliance review (Visits 4, 5, 8, and 9)
------------	--

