9.1.2.3 Visit 4 (Day 15) and Visit 5 (Day 21)

Visits 4 and 5 will occur 14 and 20 days after the first dose of IMP, respectively. A visit window of ± 1 and ± 2 days, respectively, from the scheduled visit date is permitted, but it is preferred that the visit is performed on the scheduled visit day, where possible.

Once a stable daily dose has been reached, patients should gradually decrease the interval between sprays to a target interval of approximately 1 minute between sprays. Patients should continue IMP administration at the same dose level achieved at the end of titration (i.e., their daily optimized dose) ± 1 spray divided into a morning dose and an evening dose for approximately 7 days (maintenance-dose phase). Administration of the morning and evening doses of IMP should be maintained around the same time of each day in a consistent manner in relation to food consumption, i.e., within 30 minutes after starting a snack or meal.

On Visit 5, patients will administer their morning dose of IMP with a standardized snack containing at least 300 kcal (of which approximately 30 kcal is composed of fat) at the trial site under the supervision of site staff. The IMP will not be administered in the evening of Visit 5 (Day 21).

The following assessments/procedures will be performed at these visits, unless otherwise indicated:

- MAS assessment (Visit 5 [3 hours ± 15 minutes after the first spray of the morning dose] only)
- T25FW test (Visit 5 only)
- Concomitant medications review
- AE review

- Physical examination (Visit 5 only)
- Examination of the oral mucosa
- Vital signs measurement
- 12-lead ECG (Visit 5 only)
- Clinical laboratory sampling (hematology and biochemistry) (Visit 5 only)
- PK blood sampling for IMP ([Section 9.2.12.1](#))
- MSSS-88 assessment (Visit 5 only)
- C-SSRS assessment
- IMP dosing at the investigational site (Visit 5 [morning] only)
- IMP dispensing (Visit 4 only)
- IMP collection and compliance review ([Section 9.2.16](#))

The exact time of PK blood sampling and the time of the patient's snacks and meals should be recorded.

Patients should be reminded to record their 11-point NRS spasticity score, spasm count, use of antispasticity medications, and IMP dosing in the electronic diary once daily, around the same time each day, preferably in the evening before retiring to sleep.

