10.1.3 Target Days and Visit Window

Visit windows are summarized in [Table 10.1-3](#) for efficacy data and urine drug screen collection and, in [Table 10.1-2](#) for all other safety endpoints.

When there are multiple observations within a visit window, the value closest to the target day will be analyzed (as described in [Table 10.1-1](#)).

For safety assessments, on-treatment assessments will be preferred to off-treatment ones.

In case of ties between observations located on different sides of the target, the observation with the earliest date/time will be used. In case of ties between observations located on the same side of the target, (i.e., more than one value for the same day but at different time), the observation with the earliest date/time will be used. However, in case of non-respect of wash-out period, the one done at least 7 days after last Period 1 dosing date will be preferred.

For efficacy, PRO endpoints visit windowing will apply whether patient is on or off treatment.

Table 10.1-1 Longitudinal Assessment – Analysis Day and Target Day

Treatment Period	Visit / Day	Analysis visit	Target Day (defined by period)	Observation used for analysis, if more than one exists
Screening	Visit 1 / Day -28 to -1	Screening	Day -28 to -1	Latest value
Period 1	Visit 2 / Day 1	Day 1	Day 1*	Closest to Target Day But Day 1 H0 should be before 1 st IMP intake and D1H3 should be post IMP intake
	Visit 3 / Day 8	Day 8	Day 8	Closest to Target Day
	Visit 4 / Day 15	Day 15	Day 15	Closest to Target Day
	Visit 5 / D21	D21	D21	Closest to Target Day
Period 2	Visit 6 / Day 31	Day 1	Day 1*	Closest to Target Day But Day 1 H0 should be before 1 st IMP intake and

Treatment Period	Visit / Day	Analysis visit	Target Day (defined by period)	Observation used for analysis, if more than one exists
				D1H3 should be post IMP intake.
	Visit 7 / Day 38	Day 8	Day 8	Closest to Target Day
	Visit 8 / Day 45	Day 15	Day 15	Closest to Target Day
	Visit 9 / Day 51	D21	D21	Closest to Target Day
Follow-up	Visit 10 / Day 58	Day 28	Day 28**	Closest to Target Day

H = Hours; IMP = Investigational medical product.

** Day 1 is based on the date of IRT call within each period*

*** Day 28 relative to the period where IMP is permanently discontinued thus visit is expected between Day 25 and Day 31*

Table 10.1-2 Longitudinal Assessment – Target Day and Visit Window – Part 1

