12.7 Safety Analyses

The safety analyses will be conducted during the 51-day on-treatment safety period (as described in [Section 10.1](#)) by actual treatment arm. As appropriate, the safety analyses will also be conducted during the follow-up period (as described in [Section 10.1](#)) by treatment sequence. All the safety analyses will be conducted using the Safety Analysis Set.

Some analyses of adverse events and laboratory parameters will assess the potential impact of the study drug among the subgroups presented in Table 12.7-1.

Table 12.7-1 Subgroups applied to Safety Analysis

Group Variables	Subgroup	Comments
Sex	Male Female	
Age group	≤ 18 , > 18 and ≤ 45 ≥ 46 to ≤ 65 > 65	According to patient's distribution within age, age group may be differently defined Detailed derivation is given in Section 10.10
Race	White Black or African American Asian American Indian or Alaska Native Native Hawaiian or Other Pacific Islander Other	According to patient's distribution within race some races may be grouped together
Prior cannabis use	Yes No	If it appears that one patient has missing prior cannabis use information, the missing category will be added for AE summary
Number of current antispasticity medication	0 1 2 ≥ 3	

Patient mean number of daily sprays	≤ 6 sprays, > 6 sprays and ≤ 12 sprays, > 12 sprays.	This is referring to “Patient means number of daily spray” taken during the maintenance phase (derivation as described in Section 10.8.2)
-------------------------------------	--	--

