12.7.3 Laboratory Data

The clinical safety laboratory data (hematology and biochemistry) are planned to be collected at Screening and D21 of each treatment period. In case of premature end of treatment the latest assessment collected on-treatment will be used as described in [Table 10.1-1](#).

For the purposes of summarization in both the tables and listings, all laboratory values will be converted to standardized units. The investigator and medical monitor will be provided with a list of the normal ranges used by the central clinical laboratory for all variables assayed during the trial and a statement of accreditation (or similar) for the laboratory. However, AST, ALT, GGT, ALP and total bilirubin will be summarized using SI units.

Only scheduled laboratory parameters defined in Appendix 2 and those derived from them as eGFR (as defined in [Section 10.13](#)) will be included in summary tables and figures. However unscheduled laboratories values (coming from central or local laboratories) will be used in abnormality summary tables and will be presented in listings (using categories as defined in Appendix 6).

Baseline (Screening), D21 of each treatment period and the change from baseline to D21 (end of the treatment) will be summarized using the safety analysis set, by treatment arm, separately for red blood cells parameters and white blood cells parameters, hepatobiliary parameters, renal parameters, coagulation parameters and electrolytes and proteins (as described in [Appendix 2](#)). Furthermore, AST, ALT, GGT, ALP and total bilirubin will also be summarized as a multiple of the upper limit of normal (ULN).

Laboratory hematology and biochemistry (as described in Appendix 2) abnormalities will be evaluated, on patients from the Safety Analysis Set using shift tables at D21 according to baseline status with categories based on:

- reference ranges as either normal, below the lower limit of normal (LLN) as “Low” or above the ULN as “High”,
- based on CTCAE toxicity grade using version 5.0 or higher (as defined in Appendix 4 for hematology parameters and in Appendix 5 for biochemistry parameters), presented by treatment arm.

Shift tables based on reference ranges will also be repeated for the subgroups presented in Table 12.7-1.

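### SAP rules conflict on whether the end-of-period laboratory and ECG results of patients who stop IMP early enter the by-treatment safety tables

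*SAP*

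**What the plan says.** **Schedule.** The protocol synopsis lists "12-lead ECG, and clinical laboratory blood sampling (hematology and biochemistry) (Visits 1, 5, and 9" as the collection visits. SAP 12.7.3 agrees for the laboratory: "The clinical safety laboratory data (hematology and biochemistry) are planned to be collected at Screening and D21 of each treatment period". The Safety Follow-up Visit (Protocol 9.1.5) has neither blood chemistry or hematology nor an ECG.

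**Patients who stop IMP early.** Protocol 4.1 and 9.1.4.3 encourage them to stay to the end of the period in which they stop and to have the End of Treatment Visit then. SAP Table 9.1-2 adds that no Period 2 data are collected for patients who stop in Period 1.

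**Text that leaves the late result out.** SAP 10.1.1 ends Safety Period 1 at the earliest of several dates, among them "the day before Visit 6 date and permanent end of treatment date + x days", and sets "x will be equal to 14 days for Adverse events, 4 days for C-SSRS and 0 days otherwise". SAP 12.7 states: "The safety analyses will be conducted during the 51-day on-treatment safety period". SAP 12.7.3 has a laboratory rule for early stops: "In case of premature end of treatment the latest assessment collected on-treatment will be used". The out-of-range table and the baseline-versus-last-value scatterplot in 12.7.3, and the DISH plot in 12.7.3.1, are also tied to on-treatment data.

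**Text that lets it in.** SAP 10.1.3 gives only a priority: "For safety assessments, on-treatment assessments will be preferred to off-treatment ones". Table 10.1-2 runs the D21 window for physical examination, ECG and laboratory from after the Day 1 dose to the last visit of the period, with no cut at the last dose. The by-arm liver-injury summary in 12.7.3.1 counts any post-baseline visit and links washout and post-discontinuation elevations to a treatment.

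**ECG.** SAP 12.7.5.2 summarises change to D21 and abnormalities within each treatment period, and does not mention early stops.

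**The concern.** The only scheduled sample in a period comes at its end, and the laboratory and ECG window closes on the last-dose date. A patient who stops on Day 12 and returns on Day 21 gives blood and has an ECG, but a programmer following 10.1.1, 12.7 and 12.7.3 would leave the laboratory values out of the D21 summaries, the shift tables and the out-of-range table. A programmer following 10.1.3 and Table 10.1-2 would put the same values in. The plan does not say which rule governs.

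The patients concerned are not a random subset. Protocol section 10 includes liver-enzyme criteria among the reasons for ceasing IMP, and allows cessation for adverse events that include clinically significant laboratory results. Under the exclusion reading, safety data already collected would be missing from by-arm tables for patients whose stopping may be drug-related.

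**Working it through.** The plan states no figure on this point, so there is none to reproduce. The check is day arithmetic followed by a comparison of the rules.

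**Inputs**
- x = 0 for laboratory and ECG, 4 for C-SSRS, 14 for adverse events (SAP 10.1.1).
- Visit 5 target Day 21. Protocol 9.1.2.3 says of Visits 4 and 5: "A visit window of ± 1 and ± 2 days, respectively, from the scheduled visit date is permitted". Visit 5 therefore falls on Day 19 to 23. Protocol 9.1.4.3 gives Visit 9 the same window around Day 51, which is Day 21 of Period 2.
- The permanent end-of-treatment date is taken to be the date of the last dose, in line with how SAP 10.7 derives exposure.

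**Rule.** With last dose on Day k and visit on Day v, the result is on-treatment if v ≤ k + x. An early stop is any k from 1 to v − 1.

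| Visit day v | Early last-dose days | Inside with x = 0 | Inside with x = 4 | Inside with x = 14 |
|---|---|---|---|---|
| 19 | 18 | 0 | 4 (Days 15–18) | 14 (Days 5–18) |
| 21 | 20 | 0 | 4 (Days 17–20) | 14 (Days 7–20) |
| 23 | 22 | 0 | 4 (Days 19–22) | 14 (Days 9–22) |

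With x = 0, no early stop leaves the scheduled result on-treatment. All of these visits lie inside the D21 window of Table 10.1-2, so the two rules give opposite answers for the same sample.

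**Who is unaffected.** Completers take the final dose in clinic on the visit day. For patients who go on to Period 2, Safety Period 1 is not cut at the last Period 1 dose, because only a permanent end of treatment brings it forward. A patient who stops in Period 2 keeps the Period 1 result.

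**Worked case.** Last dose of nabiximols on Day 12, abnormal laboratory value on Day 21. The gap is 21 − 12 = 9 days. An adverse event with onset that day is treatment-emergent to nabiximols, since 9 ≤ 14. The laboratory value behind it is outside the on-treatment out-of-range table, since 21 > 12 + 0.

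**Output by output, for the end-of-period result of an early stopper**

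| Output | Governing text | Result |
|---|---|---|
| D21 laboratory summaries and shift tables | 12.7.3 early-stop rule against Table 10.1-2 and 10.1.3 | Conflict |
| Out-of-range table; last-value scatterplot | 12.7.3, on-treatment | Excluded |
| DISH plot | 12.7.3.1, on-treatment safety period | Excluded |
| By-arm liver-injury summary | 12.7.3.1, any post-baseline visit | Included |
| ECG at D21 and ECG abnormalities | 12.7 against Table 10.1-2; 12.7.5.2 silent | Ambiguous |

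Two details weaken the inclusion reading without settling the matter. SAP 10.1.3 says windowing applies on or off treatment for efficacy and patient-reported endpoints, but says no such thing for safety. The D21 footnote to Table 10.1-3 (efficacy) includes off-treatment days, and Table 10.1-2 has no equivalent.

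**The case against.** The strongest reply is that the SAP already admits the sample. The window in Table 10.1-2 runs to the last visit, the on-treatment preference matters only when there is a competing value, and 10.1.1 allows exceptions to the safety period where otherwise specified. The laboratory early-stop rule does not extend to ECG. The liver-injury summary, the most safety-critical laboratory output, keeps later values. Findings judged to be adverse events get the 14-day allowance, unscheduled on-treatment values enter the abnormality tables, and all results are listed. Protocol 12.7 also requires an end-of-treatment assessment after withdrawal from treatment for an adverse event. Its timing is not given, so some samples may be close to the last dose.

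Most of this stands as a limit on the point. A reader might infer that early stoppers have no scheduled post-baseline laboratory or ECG result in any by-treatment table. The documents do not support that, for the reasons just given. The reply does not remove the conflict, however. The laboratory rule in 12.7.3 is specific and points to on-treatment values, while the out-of-range table, the scatterplot and the DISH plot are restricted in their own text. The liver-injury summary covers liver criteria only.

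**Conclusion.** The point holds as an inconsistency. For patients who permanently stop IMP early and attend the end-of-period visit, the SAP excludes the scheduled laboratory result from some by-arm outputs, includes it in another, and gives conflicting or no direction for the rest, including ECG. For Period 1 stoppers that visit supplies the only scheduled post-baseline laboratory and ECG result in the trial. This should be settled before unblinding, but it does not touch the efficacy conclusions.

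Two further inferences are tempting and not supported.
- **That abnormality rates on nabiximols are understated.** Leaving a patient out of a shift table removes that patient from those assessed as well as from any abnormal count. A late value may also have normalised, so including it could lower the rate. The direction is unknown.
- **That about 8 patients are affected**, from 68 / 0.9 = 75.6, or about 76 randomised for 68 completers. The 10% is a dropout allowance, not a rate of stopping IMP, and the SAP does not state 76. Patients who leave before the end-of-period visit may have no sample to recover, and those who leave during washout already have an on-treatment Visit 5 result.

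The documents give no IMP-discontinuation rate, so neither the number of patients nor the size of any bias can be stated. The conclusion assumes that the end-of-treatment date is the last-dose date and that no unscheduled on-treatment sample exists.

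**What to change.** State one rule in SAP 10.1.1, 12.7.3 and 12.7.5.2. When IMP is stopped early and the period has no on-treatment value, the end-of-period laboratory or ECG result fills the D21 slot. It also counts in the out-of-range, abnormality and DISH outputs, is attributed to the actual treatment of that period, and is flagged with days since last dose. On-treatment-only versions can be kept alongside if wanted.

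Changing x to 14 for these data is not needed. On its own it would still miss last-dose Days 1 to 6 for a Day 21 visit (14 of 20 early stop days captured), whereas the rule above covers every early stop with an end-of-period result.

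The cost is SAP wording and one derived flag, with no new data collection. The downside is that some values will have been taken up to about 20 days after the last dose (21 − 1 = 20 for a Day 21 visit, 22 at the late edge of the window) and may have normalised. The flag lets the reader see this.
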